1. BACKGROUND AND RATIONALE

1.1 General Introduction

The skin is a vital organ with several major functions: protection, sensation, thermoregulation, excretion, absorption, and metabolism. Any breach in skin integrity may lead to the disruption of one or more functions as well as pain, discomfort and possible infection. Some wounds may be sutured (primary intention healing) whereas open wounds may heal by secondary intention, which is a slower process. The longer a wound exists, the greater the potential for infection as it will require regular dressing changes over a period of time; a procedure that will always carry a risk of potential infection.

Depending on the healing time of a wound, it can be classified as acute or chronic:

- Those classified as acute wounds heal with little or no complications in the predicted amount of time, such as surgical, thermal and chemical or any traumatic type of wounds.
- Those classified as chronic wounds take a longer time to heal and often have different degree of complications, such as infectious, ischemic, diseases (Epidermolysis Bullosa), radiation-poisoning (therapeutic or accidental) or any ulceration type of wounds (pressure ulcer, venous leg ulcer, diabetic foot ulcer).

When wounds are extensive, unsuitable for closure by suturing, or are likely to cause physical or psychological problems through scarring, skin grafts should be considered in order to accelerate healing and minimize scarring of wounds¹.

Split-thickness skin grafting is the most frequently used reconstructive technique to repair damaged or missing skin (e.g. burns, chronic, and traumatic wounds), including

those that cannot be covered by a skin flap, which consists of skin and subcutaneous tissue that survives based on its own blood supply, or are not likely to be ameliorated by secondary intention. The wound created after harvesting the skin is called the donor site wound (DSW). Treatment of the split-thickness graft donor sites has been studied over the years, but no standard treatment for managing these sites is confirmed.

Depending on the thickness of the split skin grafting, the DSW should spontaneously re-epithelialize completely in 7 to 21 days. Optimum local care for these DSWs should facilitate the wound healing process and be cost-effective, while it should prevent associated complications, such as pain, discomfort, infection, and scarring and consider the patients' physical and mental well-being during the treatment process. Particularly pain and discomfort are reported to occur with more frequency from DSWs than on the recipient site^{2,3}.

TWB-103 is supplied as a two-component therapeutics consisting of one vial of living allogeneic fibroblasts (TWB-102 cells) and one vial of gelatin-based hydrogel (TWB-103 hydrogel). While the mechanism of healing is multi-modal, TWB-103 does not function as a barrier dressing, but rather than a "stimulus" or "aid" to wound healing. TWB-102 cells do not persist as occurs in a graft. It is believed that, upon application to the wound, the production of cytokines and growth factors by the living cells are the key factors responsible for the ability of TWB-103 to enhance healing by secondary intention.

Nonclinical studies have shown that the fibroblasts present within TWB-103 produce many of the signaling molecules, such as basic fibroblast growth factors (bFGF), platelet-derived growth factor (PDGF), and other growth factors and cytokines that are known to be beneficial to the various phases of wound healing (i.e. hemostasis, inflammation, proliferation, and remodeling). Additionally, TWB-103 can also

provide wound site a number of matrix proteins that play key structural roles in skin and in healing.

1.2 Rationale and Justification for the Study

1.2.1 Rationale for the Study Purpose

Transwell Biotech Co., Ltd. (TWBIO) seeks approval of an Investigative New Drug (IND) for TWB-103. Specifically, TWBIO is seeking regulatory permission to apply the product for first-time-in-human for managing surgical and donor site wounds in adults due to autografting procedure. The purpose of the present phase I/II study is to explore the safety and efficacy profiles of TWB-103 in split-thickness skin graft DSW. This study will be conducted via a randomized, double-blind, additional evaluator-blind, placebo-controlled, multi-center, multi-nation (Taiwan and Japan), parallel fashion.

1.2.2 Rationale for Doses Selected

TWB-103 has not yet been previously approved by any regulatory authorities in the world. However, the overall safety of TWB-103 has been characterized in the animal models of cutaneous wounds. Nonclinical studies of TWB-103 in the burn indication have not been performed as the general acute cutaneous wounds have more similarities than differences to the wounds of the donor site. The nonclinical set of data on TWB-103 includes product characterization, cell migration, tumorigenicity and immune-toxicity. The results of these studies do not suggest a potential for immunological, toxicological, or oncogenic risks. Moreover, efficacy is further supported by more than 15 years of human use safety experience in Switzerland of FE002-SK2, the same cell line making TWB-103.

1.2.3 Rationale for Study Population

The study population designed to be enrolled are patients aged at 20-65 years old presenting a split-thickness skin graft DSW with a minimum size of 15 cm² but no more than 100 cm², with a minimum width of 3 cm, and with an approximate thickness of 0.010~0.012 inches. Since TWB-103 is believed to have the ability to regenerate functional skin tissue by modulating and improving secondary intention wound healing, the study population is therefore selected.

1.2.4 Rationale for Study Design

This is a phase I/II study intending to explore the safety and efficacy of TWB-103 in split-thickness skin graft DSW by adding on TWB-103 to TegadermTM, the standard of wound care to compare with placebo+TegadermTM. In this study, TWB-103 will be applied as an adjuvant therapy besides TegadermTM for safety concern since this is a first-time-in-human study for TWB-103 even though TWB-103 is believed to be relatively safe and also for ethical concern. The ethical issue is also concerned with employing placebo+TegadermTM as a control. To avoid systematic bias, the study is designed as a double-blind, additional evaluator-blind, randomized study.

2. OBJECTIVES AND ENDPOINTS

2.1 Objectives

2.1.1 Primary Objectives

1. To evaluate the safety for Phase I of TWB-103 in split-thickness skin graft donor site wounds (DSW) for Phase I in terms of incidence of treatment-related AEs and SAEs (including infections and bleeding)
2. To evaluate the efficacy for Phase I+II of TWB-103 in split-thickness skin graft donor site wounds (DSW) in terms of the healing time from DSW creation to 100% re-epithelialization

2.1.2 Secondary Objectives

1. To evaluate the efficacy of TWB-103 in split-thickness skin graft donor site wounds (DSW) in secondary efficacy endpoints
2. To evaluate the safety of TWB-103 in split-thickness skin graft donor site wounds (DSW) in secondary safety endpoints

2.2 Endpoints

2.2.1. Primary endpoints

The primary endpoint for this study is:

Phase I

Safety:

Incidence of treatment-related AEs and SAEs (including infections and bleeding)

Phase I+II

Efficacy:

The healing time from DSW creation to the first 100% re-epithelialization with confirmation for at least 10 days apart, assessed by the investigator

2.2.2. Secondary endpoints

The endpoints used to achieve the secondary objectives of this study are listed below:

Phase I+II

Efficacy:

1. The healing time from DSW creation to the first 100% re-epithelialization with confirmation for at least 10 days apart, assessed by the first additional evaluator
2. The healing rates (complete wound closure) of patients at Days 7, 10 and 14 after DSW creation

Note: Complete wound closure is defined as skin 100% re-epithelialization without drainage or dressing requirements.

3. The healing percentage of wounds (ratio of healing area and original area) at Days 7, 10 and 14 after DSW creation
4. The pain change from baseline to post-wound creation visits based on short-form McGill pain questionnaire score

Safety:

1. Incidence of treatment-related AEs and SAEs (including infections and bleeding)

2. Incidence of AEs and SAEs

3. Changes in post-treatment physical examination, vital signs, and general laboratory assessment compared to baseline

Note: The investigator will determine the end of treatment based on the healing progress.

Wound healing will be assessed based on the wound observation by the investigator and an additional evaluator. An additional evaluator who is not aware of the treatment given will evaluate based on photos of the wound. The additional evaluator will receive photos of the wound from CRO and will return the assessment to CRO. A second additional evaluator, who is also blinded, will be requested when the discrepancy occurs between the investigator and the first additional evaluator in the determination of 100% re-epithelialization.

3. STUDY POPULATION

3.1 The Number of Patients to Be Enrolled

The sample size is determined to be 15 versus 15 evaluable (per-protocol for Phase I+II) patients (1:1 ratio) for Treatment versus Control groups, 30 evaluable patients in total. To ensure the completion of 30 evaluable patients, around 36 patients will be recruited.

3.2 Inclusion Criteria

A patient is eligible for the study if all of the following apply:

1. Female/male patients, aged 20-65 years old
2. Presenting a split-thickness skin graft donor site wound with a minimum size of 15 cm² but no more than 100 cm², with a minimum width of 3 cm and with an approximate thickness of 0.010~0.012 inches. The graft cannot be harvested from a site from which a skin graft was previously obtained.
3. If the primary wound is a result of a thermal or chemical burn, the total body surface area of the said wound must be less than 15%.

Note: The burn area is estimated based on the method used at the local site. The Rule of Nines Chart (1% body surface area equals one patient's palm size) or Lund and Browder Chart are acceptable.

4. Females of childbearing potential must have a documented negative serum pregnancy test done at the screening visit, which is within 2 weeks prior the DSW creation and the treatment
5. Both male and female patients must agree to use highly effective contraceptives from signing informed consent to 30 days after the last dose administration. Acceptable contraceptive forms include:

- a. Established use of oral, injected or implanted hormonal methods of contraception
- b. Placement of an intrauterine device (IUD) or intrauterine system (IUS)
- c. Barrier methods of contraception: Condom or occlusive cap (diaphragm or cervical/vault caps)

6. Willing to comply with the study protocol and has signed the Informed Consent Form

Note: The rationale for the inclusion criteria is described as below.

1. The lower limit of age, 20 years old is set as the age to participate in clinical trial by self-responsibility (the legal age of consent is 20 years old in Taiwan and Japan). Upper limit 65 years old is set because elderly patients tend to be poor in compliance and have poor skin quality.
2. Maximum size of DSW, 100 cm², is set by the standard of the investigational product, and a minimum size of 15 cm² is set considering that smaller DSW can heal easily and the existing standard treatment is sufficient. Minimum width of 3 cm is defined based on commonly medical appliance used for DSW creation. The thickness (0.010 - 0.012 inches) of the split skin grafting is defined based on clinical practice. And then, to minimize the complexity of safety and efficacy evaluation, the skin graft should be obtained from the area that has no previous use for skin graft.
3. To ensure the safety of patients, only mild burn patient (total burn surface area less than 15%) can be considered for recruitment
- 4-5. The criteria are to ensure the safety of patients, patient's partners, fetuses and infants.
6. It is to confirm that the patient complies with this study protocol.

3.3 Exclusion Criteria

Any patient meeting any of the exclusion criteria will be excluded from study participation.

1. Female patients who are pregnant or lactating or planning a pregnancy and any male patient whose partner (wife) planning a pregnancy from signing informed consent to 30 days after the last dose administration.
2. Clinically significant disease or condition that may compromise graft taken and/or donor site healing (e.g. the presence of a bleeding disorder, capillary fragility, venous or arterial disorder directly affecting the donor site to be treated, known or suspected systemic malignancies, human immunodeficiency virus infection, renal or liver disease, uncontrolled diabetes mellitus, thrombocytopenia, vasculitis, poor nutritional status).
3. Patients who are currently receiving or have received the following treatments within 4 weeks prior to Screening Visit are excluded from the study:
 - a) systemic, or inhaled corticosteroids or immunosuppressant agents; or
 - b) therapeutic doses of anticoagulants (e.g. Coumadin, Heparin, low molecular weight Heparin) for pre-existing medical conditions, for whom a dose interruption from Screening through the end of the study period is contraindicated.
4. Autoimmune disease, e.g. lupus erythematosus, multiple sclerosis.
5. Hematologic disease, malignancy or hypo-immunity.
6. History of HIV or congenital immunodeficiency.
Note: HIV = human immunodeficiency virus
7. History of alcoholism or drug abuse.
8. Have used any tobacco product within 1 week prior to Day 0.
9. Patients previously treated with any cell-based product, including autologous tissue at the treatment site.

10. Received an investigational drug, device or biological/bioactive treatment within 30 days prior to Screening Visit.
11. Any clinical condition or significant concurrent disease judged by the investigator to complicate the evaluation of the trial treatment.
12. History of sensitivity to bovine or porcine origin of materials, or human serum albumin.
13. DSWs located in the face, over joints, lower legs or the buttocks
14. Any of the following hematologic abnormalities:
 - a. Hemoglobin < 10.0 g/dL
 - b. ANC < 1,500/ μ L,
 - c. Platelets < 75,000 / μ L
15. Any of the following serum chemistry abnormalities:
 - a. Total bilirubin > 1.5 \times ULN,
 - b. AST or ALT > 3 \times ULN,
 - c. γ -GT > 2.5 x ULN,
 - d. Alk-P > 2.5 x ULN,
 - e. Serum albumin < 2.7 g/dL,
 - f. Creatinine > 1.5 x ULN
- g. Any other \geq Grade 2 laboratory abnormality (based on CTCAE) at baseline (other than those listed above)
16. DSWs in area with active skin infection or with skin condition that is considered highly susceptible to infection judged by the investigator

Note: The rationale for the exclusion criteria is described as below.

1. It is to ensure the safety of patients, patient's partners, fetuses and infants.
- 2-7., 12., 14-15. Criteria are set to ensure the safety of patients due to the potential increased chance of infection, prolonged wound closure, immunological over-reaction, or other complications resulted from these conditions.
- 3., 5-8. These conditions and habits may affect the efficacy evaluation of investigational product.
- 9-11., 16. Those are to minimize the complexity of safety and efficacy evaluation.
13. DSW located on face is excluded with ethical consideration. Other locations are excluded to minimize the complexity of safety and efficacy evaluation.

3.4 Withdrawal Criteria

Patients may be withdrawn from the trial due to any of the following conditions:

1. The patient decides to withdraw her/his informed consent form.
2. Investigator considers that the patient is no longer physically and/or psychologically feasible to remain in the study.
3. The patient refuses to proceed with critical measures for the study endpoints, defined as all variables required for primary endpoint evaluation.
4. The patient has lost to follow-up

The reasons for discontinuation must be recorded in the Case Report Form (CRF) and in the patient's medical records for all early terminated cases. All study participants withdrawn from the study before Day 28 will finish assessments of Visit 7 (Day 28), except the application and dispensation of TegadermTM. If the patient has received TegadermTM from the visit before withdrawal, the return of TegadermTM should be made. For patients who have initially scheduled Day 42 visit but make the decision between Day 28 to Day 42 to withdraw from the study, he/she should be encouraged to complete assessments planned for Day 42 visit at the earliest date convenient for the

patients. If patients have entered the long-term follow-up period (i.e. after Day 28 or Day 42 if scheduled) and the decision of withdrawal is confirmed, effort must be made to understand and record the reason of withdrawal. If a patient is discontinued due to an AE, every effort will be made to follow the event until resolution.

3.5 Patient Replacement

All patients who drop out of the study will not be replaced. New patients will be screened with a newly assigned patient number until the target evaluable patients are reached in this study.

3.6 Concomitant Treatments

All medications and supplements taken by the study participant beginning four weeks prior to Screening Visit till Visit 8 will be recorded on the appropriate page of the Case Report Form (CRF). This record will include the name of the medication, frequency, unit dose, dates of the drug was started and stopped, and the indication for the use of the drug.

Patients are allowed to receive routinely used medications or treatments for other indications which is judged by the investigator as not affecting the efficacy and safety assessments of this study.

- Prohibited Medications/Treatment

- a) systemic, or inhaled corticosteroids or immunosuppressant, chemotherapeutic agents
- b) therapeutic doses of anticoagulants (e.g. Coumadin, Heparin, low molecular weight Heparin)
- c) Any treatment/therapy applied to wound area that may affect the efficacy evaluation of study medication at the investigator's discretion

d) Any treatments containing povidone-iodine, chlorhexidine, polymyxin and mycostatin, for DSW.

4. STUDY DESIGN

This study will be designed in a Phase I/II randomized, double-blind, additional evaluator-blind, placebo-controlled, multi-center, multi-nation (Taiwan and Japan), parallel manner. This study is to evaluate the safety and efficacy of the TWB-103 in adult patients with split-thickness skin graft donor site wounds (DSW). The study will recruit 30 evaluable patients, approximately up to 36 patients to be recruited to complete a total of 30 evaluable patients. Eligible patients will be randomly assigned in 1:1 ratio to one of the following groups:

Treatment Group:

TWB-103 add-on TegadermTM till 100% re-epithelialization or up to 10 days, whichever comes first, followed by TegadermTM alone application from Day 10 to Day 14 if failing to achieve 100% re-epithelialization by Day 10. If 100% re-epithelialization is not observed on Day 14 (the end of treatment), patients will have application of TegadermTM up to Day 28.

Control Group:

Placebo+TegadermTM till 100% re-epithelialization or up to 10 days, whichever comes first, followed by TegadermTM alone application from Day 10 to Day 14 if failing to achieve 100% re-epithelialization by Day 10. If 100% re-epithelialization is not observed on Day 14 (the end of treatment), patients will have application of TegadermTM up to Day 28.

Note:

1. TegadermTM will be renewed at each visit between Visit 3 (Day 3) to Visit 7 (Day 28) if 100% re-epithelialization is not observed. Whenever TegadermTM falls off from DSW site, new TegadermTM should be applied immediately. If necessary, drainage is allowed, but re-application of TWB-103 or placebo is not necessary in this case.

2. If the first 100% re-epithelialization is observed on Day 28, patients will be scheduled Day 42 follow-up and dispensed with Tegaderm™.
3. If the first 100% re-epithelialization is not observed on Day 28, patients will receive the application of Tegaderm™ on site for protection of wound site and/or have other appropriate treatment at the investigator's discretion. The DSWs will be followed till 100% re-epithelialization.
4. To prevent the itchiness and skin reaction caused by the long-term usage of Tegaderm™, Vaseline Gauze or Non-Stick Gauze such as silastic foam dressings can be used on and after Day 14 at the investigator's discretion.

In Phase I proportion, eligible patients will be recruited sequentially with one week staggering in the initiation of study treatment. Eligible patients will also be randomized into 1:1 ratio into one of Treatment (TWB-103+Tegaderm™) and Control (placebo+Tegaderm™) groups. Phase I plan to recruit 3 evaluable TWB-103+Tegaderm™ treated and 3 evaluable placebo+Tegaderm™ treated patients. Patients in phase I are considered as evaluable when (1) he/she receives at least one dose and has follow-up evaluation at least 14 days after first dose or (2) he/she receives at least one dose and has early withdrawn due to safety reasons before Day 28. When all of those 6 evaluable patients complete the planned treatment period (14 days or till first 100% re-epithelialization, which comes first), the recruitment of patients will be temporarily stopped for 14 days for safety observation. The safety data of TWB-103 before and on Day 28 Visit will be reviewed by the sponsor and the principal investigator. If no safety issue of TWB-103 is decided, the study will enter Phase II portion and eligible patients will be randomized into 1:1 ratio into one of Treatment and Control groups.

Each patient will have treatment for up to 14 days or to the day of 100% re-epithelialization, whichever comes first. Patients assigned to the Treatment Group will receive TWB-103 add-on Tegaderm™ till 100% re-epithelialization or up to 10 days,

whichever comes first and will receive Tegaderm™ alone from Day 10 to Day 14 if re-epithelialization can not be attained by Day 10. Patients assigned to the Control Group will receive placebo+Tegaderm™ till 100% re-epithelialization or up to 10 days, whichever comes first and will receive Tegaderm™ alone from Day 10 to Day 14 if re-epithelialization can not be attained by Day 10. Patients from either group (treatment or control) will have application of Tegaderm™ alone up to Day 28 if 100% re-epithelialization of DSWs is not observed on Day 14 (end of treatment).

Patients will be required to attend scheduled visits at Screening, Day 0 (treatment start day), Day 3, Day 7, Day 10, Day 14 (end of treatment). In case patients achieve 100% re-epithelialization before or at Day 10, patients will finish up the assessments on the day with 100% re-epithelialization. This day of 100% re-epithelialization will be the end of treatment and the remaining scheduled treatment visits, if applicable, will be dismissed.

All subjects are scheduled to attend a follow-up visit on Day 28 to evaluate the status of the target wound and then enter a 360-day follow-up phase. If the complete wound closure occurs by Day 14, the re-confirmation of wound closure should be performed on Day 28 follow-up. In the case that complete wound closure occurs at some point between Day 14 and Day 28, an additional follow-up visit will be scheduled on Day 42 for the re-confirmation before subject enters the 360-day follow-up phase. If the complete wound closure is not observed on Day 28, patients will have other appropriate treatment at the investigator's discretion. The DSWs will be followed till 100% re-epithelialization.

During the 360-day follow-up, four follow-up visits will be scheduled at 90 ± 14 days, 180 ± 14 days, 270 ± 14 days and 360 ± 14 days following the subject's Day 28 visit (if no

Day 42 visit) or Day 42 visit. In total, 5~6 follow-up visits will be scheduled in this study for all randomized subjects.

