2. When DSW reaches 100% re-epithelialization by Day 14, a re-confirmation of wound closure will be performed on Day 28.										

3. Day 42 visit is only for patients whose DSWs do not reach to 100% re-epithelialization on Day 14 but heal on Day 28 as a re-confirmation.
4. For patients whose visit 8 (Day 42) is scheduled, these visits will be arranged at 90, 180, 270 and 360 days after visit 8 (Day 42); otherwise, these follow-ups will be planned at 90, 180, 270 and 360 days after visit 7 (Day 28). These long-term follow-ups should be scheduled even if 100% re-epithelialization is not observed on Day 28 or Day 42.
5. For treatment group: TWB-103+TegadermTM. For the control group: placebo+TegadermTM. The application will be discontinued when the 100% re-epithelialization of DSW is observed by the investigator.
6. The size of TegadermTM to be used for each patient will be determined by the investigator based on the size of DSW. Whenever TegadermTM falls off from DSW site, new TegadermTM should be applied immediately. If necessary, drainage is allowed, but re-application of TWB-103 or placebo is not necessary in this case.
7. TegadermTM is applied to the wound site after the investigator has finished the wound assessment if the DSW has not reached 100% re-epithelialization, regardless the original group assignment.
8. TegadermTM is dispensed to the patient regardless of the condition of DSWs. Patients are advised to apply TegadermTM to DSW site if the wound open remains or reappears, and to re-apply new TegadermTM every 2~3 days till next visit or wound closure. The amount of TegadermTM dispensed should be adequate for patient's use till next visit.
9. Unused TegadermTM is returned to the study site if TegadermTM is dispensed to the patient at the previous visit. Re-dispensing of unused TegadermTM to the same patient is allowed when the primary package of TegadermTM remains intact.
10. The patient will receive the application of TegadermTM on site for protection of wound site and/or start with other treatment recommended by the investigator if DSW does not reach 100% re-epithelialization by Day 28.

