6.11 Wound assessment

The wound assessment will be measured at all scheduled visits except the Screening Visit.

From Visit 2 (Day 0) to Visit 8 (Day 42), the investigator will determine the end of treatment based on the healing progress. Wound healing will be assessed based on the wound observation by the investigator and an additional evaluator. An additional evaluator who is not aware of the treatment given will evaluate based on photos of the wound. The additional evaluator will receive photos of the wound from CRO and will return the assessment to CRO. A second additional evaluator, who is also blinded, will

be requested when the discrepancy occurs between investigator and the first additional evaluator in the determination of 100% re-epithelialization.

The photos of wound will be taken under the following guidelines.

- (a) Cameras and rulers with the same brand and model will be used throughout the study.
- (b) The study staff who are trained will be in charge of taking photos following the guidelines for each study center.
- (c) Two different photos will be taken for each wound at each visit: one for the calculation of wound healing and the other as the reference of the wound location relative to the body part.
- (d) The wound area shown in the photo specific for calculation purpose, along with the provided ruler, should have sufficient size and quality for evaluation.
- (e) Images will be processed by the software, Image J.
- (f) The investigator and evaluator(s) will select the boundary of said wound in the photo manually and by the wand tool in Image J.
- (g) Calculate the wound size by Image J based on the area selected.
- (h) The healing percentage of wounds will be calculated by the ratio of healing area and original area (Day 0).

Complete wound closure is defined as skin 100% re-epithelialization without drainage or dressing requirements. Wound closure should be re-confirmed on Day 28 when the complete wound closure occurs by Day 14, or on Day 42 in the case that complete wound closure occurs at some point between Day 14 and Day 28.

During the 360 days of follow-up (Visit 9~12), recording of 100% re-epithelialization and the area of target wound are not required. Instead, potential long-term adverse

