If patient develops grade 2 or above SAEs and should exit the study prematurely before Day 14, he/she should be excluded from the primary efficacy analysis, because early censor will result in under estimation of the healing time while treatment group (TWB-103+TegadermTM) is prone to have higher risk of developing treatment related SAE.

In the cases of TWB-103/placebo discontinuation due to allergic reaction or infection, wound assessments performed after onset of allergic reaction or infection will be excluded from statistical analysis.

Healing rates (complete wound closure) of patients at Days 7, 10 and 14 after DSW creation will be analyzed by CMH test. Healing percentage of wounds (ratio of healing and original areas) at Days 7, 10 and 14 after DSW creation will be analyzed by Analysis of variance (ANOVA) model with treatment group and country as factor. Score on short-form McGill pain questionnaire will be analyzed by using Analysis of covariance (ANCOVA) model with treatment group and country as factor and baseline characteristics as covariate. Vancouver Scar Scale will be analyzed by Wilcoxon ranked sum test. The score in each category (pigmentation, vascularity, pliability and height) and the sum score of all category in Vancouver Scar Scale will be analyzed.

All treatment group comparisons will be conducted with significance level of 0.05, using 2-tailed tests.

Demographics and baseline characteristics will be summarized for each group/country by using descriptive statistics.

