10.2.5 Missing data estimation

No missing data imputation will be applied for this study.

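### Patients healed by Day 10 get no Day 14 healing percentage under the plan as written, so the Day 14 comparison omits them because they healed

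*Combined protocol and SAP*

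**What the plan says.** The dismissal rule stands in three places with the same effect: section 4, note 4 under Study Visits in the Protocol Summary, and footnote 12 of the Schedule of Assessments. It applies to patients who reach 100% re-epithelialization before or at Day 10: "This day of 100% re-epithelialization will be the end of treatment and the remaining scheduled treatment visits, if applicable, will be dismissed". Day 14 is the end-of-treatment visit (section 7.4), so it is among the visits dismissed. The investigator's judgement governs; footnote 5 says of the study product "The application will be discontinued when the 100% re-epithelialization of DSW is observed by the investigator".

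Section 2.2.2 nevertheless lists as a secondary efficacy endpoint "The healing percentage of wounds (ratio of healing area and original area) at Days 7, 10 and 14 after DSW creation", and section 10.2.2 assigns it an ANOVA at those three days. The percentage comes from the wound area traced on a photograph, relative to the Day 0 area; section 6.11 says "Two different photos will be taken for each wound at each visit". For the companion endpoint, section 10.2.2 says "Healing rates (complete wound closure) of patients at Days 7, 10 and 14 after DSW creation will be analyzed by CMH test". Section 10.2.5 reads in full on missing values: "No missing data imputation will be applied for this study".

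**The concern.** A patient healed at Day 10 has no Day 14 visit, so no Day 14 photo and no Day 14 percentage. A patient healed at Day 7 lacks Day 10 as well. With imputation barred, the Day 14 ANOVA compares only patients whose wounds were still open at Day 10. Membership of that group is itself an outcome of treatment, so the comparison is no longer between the groups as randomized, and the better a treatment works the more of its patients drop out of the test.

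The plan also leaves room for disagreement. One statistician would enter 100% for these patients as self-evident, another would follow 10.2.5 and leave them out. The two would report different denominators and different p-values, and if the choice is made after unblinding it is open to the charge of being driven by the data.

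**Working it through.** **1. Can another scheduled visit supply the Day 14 value?** From the stated windows: Day 10 ± 1 covers Days 9 to 11, Day 14 ± 2 covers Days 12 to 16, and Day 28 ± 3 covers Days 25 to 31. None overlaps Days 12 to 16, so no other scheduled visit can. Unscheduled visits (section 4.3.4) happen only on medical need.

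**2. Does any other rule supply it?** Section 10.2.2 makes visits after healing irrelevant, but for healing time only. The per-protocol definition in 10.2.1 accepts first 100% re-epithelialization in place of the Day 14 evaluation, which keeps early healers in the population but gives them no Day 14 value. Neither fills the gap.

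**3. How many patients, and what power?** The plan states no effect size, SD or power; section 10.1 calls the sample size arbitrary. There is therefore no figure of the plan's to reproduce. Section 1.1 says only that these wounds should heal in 7 to 21 days. Everything below is assumed:
- healing times lognormal, SD(log) 0.35, 15 per arm;
- healed area linear in time, so Day 14 percentage = min(100, 100 × 14/T) for healing time T;
- pooled two-sample t-test, two-sided 0.05, country factor omitted;
- as-written analysis: drop patients with T ≤ 10.

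Expected number without a Day 14 value = 15 × Φ(ln(10/median)/0.35). For a median of 10 this is 15 × Φ(0) = 7.5. For a median of 14 it is 15 × Φ(−0.961) = 15 × 0.168 = 2.5.

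| Median days, TWB-103 v control | Patients with no Day 14 value | Power, all patients | Power, as written |
|---|---|---|---|
| 10 v 14 | 7.5 v 2.5 | 0.48 | 0.18 |
| 11 v 14 | 5.9 v 2.5 | 0.30 | 0.15 |
| 12 v 14 | 4.5 v 2.5 | 0.16 | 0.10 |
| 14 v 18 | 2.5 v 0.7 | 0.42 | 0.31 |
| 16 v 20 | 1.3 v 0.4 | 0.37 | 0.31 |

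For medians 10 v 14, the loss persists when SD(log) is varied: 0.79 to 0.31 at SD 0.20, and 0.30 to 0.12 at SD 0.50. At 16 v 20 with SD 0.25 it is small, 0.64 to 0.61.

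**4. What happens to the estimate?** In this model, little: for medians 10 v 14 the mean difference is 8.7 points with all patients and 8.3 as written, while its SD rises from 4.5 to 6.0.

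That does not hold for every healing pattern. Take 15 per arm, split as healed by Day 10 / first healed at Day 14 / still open: TWB-103 9/2/4, control 3/5/7, with open wounds assumed 85% healed.
- All patients, healed counted as 100%: TWB-103 (11 × 100 + 4 × 85)/15 = 96.0; control (8 × 100 + 7 × 85)/15 = 93.0; difference +3.0.
- As written: TWB-103 (2 × 100 + 4 × 85)/6 = 90.0; control (5 × 100 + 7 × 85)/12 = 91.25; difference −1.25.

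**5. Other days.** At Day 10 with medians 10 v 14, 2.3 v 0.4 patients are lost and power falls from 0.67 to 0.54. Day 7 would be lost only to a patient healed at Day 3.

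**The case against.** *Anyone would enter 100% for a healed wound.* That is probably the intent, and the per-protocol definition shows that early healers were foreseen. But no sentence says so, and 10.2.5 says the opposite without exception. Nor is a healed wound assumed to stay healed: section 4.3.4 and footnote 8 both foresee re-opening.

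*The healing-day assessment is the end-of-treatment assessment, so it serves as the Day 14 value.* The endpoint is tied to days after wound creation, not to end of treatment, and no text makes that transfer.

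*The closure rate is equally affected.* A reader might infer this, because section 10.2.2 says *at* rather than *by* Day 14. The documents do not support it as a second defect. Elsewhere they speak of closure occurring by Day 14, as in section 4: "If the complete wound closure occurs by Day 14, the re-confirmation of wound closure should be performed on Day 28 follow-up". On that cumulative reading, closure recorded at an earlier visit counts at Day 14 and the gap disappears. This objection stands; only a clarification is needed.

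*The striking scenarios assume fast healing.* This also stands. Slower medians fit the 7 to 21 day range equally well and give a much smaller loss, as the table shows.

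*These are secondary endpoints in a study whose size is arbitrary and whose power is low in any case.* True, and it limits the importance of the point. It does not justify a rule that removes patients from an efficacy test because they healed, when correcting it costs only wording.

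**Conclusion.** The point holds for healing percentage, mainly at Day 14. The plan's rules, taken together, exclude early healers from that ANOVA and nothing in the text restores them. Under the assumed model the cost in Day 14 power runs from 0.37 to 0.31 (medians 16 v 20 days) up to 0.48 to 0.18 (medians 10 v 14). No healing rate in these figures comes from the documents.

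Three stronger conclusions should not be drawn. The primary analysis is not affected, since healing time runs to the first healing date and section 10.2.2 disregards later visits for it. False-positive risk is not inflated in the cases run: with equal medians, the type I error of the Day 14 percentage test is 0.032 as written against 0.024 with all patients (10 v 10 days), and 0.049 under both (14 v 14). And a consistent bias against TWB-103 is not shown: the mean difference is nearly unchanged in the lognormal model, and shrinks or reverses only under particular patterns such as front-loaded healing.

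This should be fixed, as a correction to the secondary analyses of a small exploratory study.

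**What to change.** In section 10.2.2, with a matching exception in 10.2.5, state before unblinding:

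- A patient whose visits were dismissed for investigator-assessed 100% re-epithelialization stays in the analysis with healing percentage 100% at each dismissed time point through Day 14, unless a re-opening is recorded.
- This analysis uses the investigator's assessment. Section 6.11 has both the investigator and the evaluators trace the wound, and the endpoint names no assessor, so any analysis of an evaluator's traced area should carry forward that evaluator's own last value.
- The closure rate at Days 7, 10 and 14 is cumulative: closed if the full definition (no drainage and no dressing requirement as well as 100% re-epithelialization) was met at or before that day, otherwise not closed. This is needed because dismissal is triggered by re-epithelialization alone.
- All other missing assessments, and those excluded after allergic reaction or infection, stay under the existing rules.

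The cost is wording only, with no added visits or procedures. The downside is that a transient re-opening before Day 14 that nobody recorded would count as healed. Footnote 8 lets patients re-cover a reappearing wound themselves, so the Day 28 re-confirmation cannot fully exclude this.
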